7.3.3. Randomization and Blinding

Upon determination that a subject meets all eligibility criteria, the subject will be randomized on Study Day -1 to receive either CRV431 or matching placebo in a 2:1 subject ratio (12 CRV431 75mg to 6 matching placebo and 12 CRV431 225mg to 6 matching placebo) in accordance with a computer-generated randomization schedule generated by a non-study statistician. Using this randomization schedule, pharmacy staff or designee will assign treatment sequentially to each eligible subject within a given cohort.

This is a single blind study where the investigator and sponsor are unblinded. However, the subject is blinded and will not know if he or she will receive CRV431 or matching placebo.

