7.7. Safety Criteria for Adjustment or Stopping Doses

7.7.1. Individual Subject Criteria

If any of the criteria below are met by an individual subject, then no further dosing will occur at any of the study sites until a review of all available safety information is performed by the DSMB, Medical Monitor, and Sponsor. Appropriate Regulatory Agencies and Ethics Committees will be informed as applicable. If it is later determined that further dosing can be performed safely then an application for a substantial protocol amendment will be submitted to the appropriate Regulatory Agencies and Ethics Committees, if applicable. Stopping criteria for an individual subject includes:

- Grade 3 or higher CTCAE AEs possibly or probably related to study drug as determined by the investigator and sponsor;
- Grade 4 CTCAE AEs regardless of relation to study drug as determined by the investigator and sponsor;
- Any SAEs thought to be related to the study drug as determined by the investigator and sponsor.

For subjects experiencing any hepatic AEs or SAEs judged by the investigator or sponsor to be related to study drug, the investigator, DSMB, Medical Monitor and Sponsor will review all available safety data and make a determination to proceed with one of the following options:

- If the event was a drug-induced liver injury (DILI), considered as increases in aminotransferases (AT) $>3 \times$ ULN or $>3 \times$ baseline where baseline is defined as the average values of Screening and Day -1, no additional subjects will be dosed until it is determined that it is safe to proceed and in addition the frequency of blood chemistries will increase to daily, if appropriate.

- Repeat testing of ALT, AST, ALP, TBL will be performed within 48-72 hours to confirm the abnormality.
- If there are persistent elevations of AT > 3 x ULN or a 2-fold increase above baseline values (for those subjects with elevated values prior to drug exposure) upon repeat testing then close observation visits should be implemented and/or discontinuation of drug should be considered. Close Observations are described in Section 7.8.
- If the event was not a DILI, as defined above, one of the following actions will be taken:
 - Dose an entire additional cohort at the same or lower dose than the dose taken by the subject that experienced the event in question;
 - Continue to pause the study, until it is determined, that it is safe to proceed.

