7.8. Close Observation

Upon detection and confirmation of early signs of possible DILI (see Section 7.7.1), close observation should be initiated immediately.

Close observation will include the following:

- Repeating liver enzyme and serum bilirubin tests 2 or 3-times weekly. The frequency of retesting can decrease to once a week or less if abnormalities stabilize or the trial drug has been discontinued and the subject is asymptomatic;
- Obtaining a more detailed history of symptoms and prior or concurrent diseases;
- Obtaining a history of concomitant drug use including non-prescription medications and herbal and dietary supplement preparations, alcohol use, recreational drug use, and special diets;

- Ruling out acute viral hepatitis types A, B, C, D, and E, autoimmune or alcoholic hepatitis, hypoxic/ischemic hepatopathy, and biliary tract disease;
- Obtaining a history of exposure to environmental chemical agents;
- Obtaining additional tests to evaluate liver function, as appropriate (e.g., INR, direct bilirubin);
- Consider gastroenterology or hepatology consultations;
- Consider liver biopsy.

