11.1.6.2. Blood Chemistry

Samples will be collected before study drug dosing and after at least an 8-hour fast; however, in case of an early termination or recheck, subject fasting is not required prior to sample collection. The following tests will be performed:

- ALT
- Albumin
- ALP^a
- Amylase, total^a or pancreatic amylase
- Anion gap
- AST
- Bicarbonate
- Bilirubin (total, unconjugated, conjugated)
- Blood urea nitrogen
- Calcium
- Chloride
- Cholesterol (total, high-density lipoprotein [HDL], and low-density lipoprotein [LDL])
- Creatinine
- Creatine kinase^b
- eGFR, using CKD-EPI method
- Glucose
- HbA1c^c
- Lipase
- Phosphorus
- Potassium
- Sodium
- Triglycerides

^a Reflex fractionation, if greater than ULN

^b Reflex fractionation if greater than critical value

^c HbA1c will be collected at Screening, D28, EOS and ET

Subjects with normal ALT and bilirubin at baseline who have ALT >3 x ULN and bilirubin >2 x ULN OR subjects with elevated ALT at baseline who have ALT > 10 x baseline value and bilirubin >2 x ULN will also have serum gamma-glutamyltransferase (GGT) determined at the time these abnormalities are discovered. For these subjects, GGT may be repeated, as clinically indicated.

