4.3 Assessment Windows

For the purpose of listing and summarizing data, the time-in-study for each subject observation will be defined using study days as defined in the Schedule of Events (Appendix A). No analysis windows are planned for the study regarding data collected outside the protocol specified windows. All data will be included in the analysis based on the visit as it is recorded in the database.

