7.2.5 Adverse Event Summaries

All AEs (serious and non-serious) occurring after completion of the informed consent process and before the end of study, regardless of relationship to study drug, will be included and classified by SOC and PT using the Medical Dictionary for Regulatory Activities (MedDRA).

For treatment-emergent AEs (TEAEs), the following will be summarized and presented for the safety analysis set:

- i. An overall summary of TEAEs, which includes:
 - a. the number and percentage of subjects experiencing a TEAE
 - b. the number and percentage of subjects experiencing a TEAE by strongest relationship to study medication
 - c. the number and percentage of subjects experiencing a TEAE by greatest severity
 - d. the number and percentage of subjects experiencing a TEAE leading to study withdrawal
 - e. the number and percentage of subjects experiencing a treatment emergent SAE (TESAE)
- ii. the number and percentage of subjects experiencing a TEAE by SOC and PT

- iii. the number and percentage of subjects experiencing a TEAE by SOC, PT and the highest severity
- iv. the number and percentage of subjects experiencing a TEAE by SOC, PT and the strongest relationship to study medication
- v. the number and percentage of subjects experiencing a TESAE by SOC and PT
- vi. the number and percentage of subjects experiencing a TEAE leading to study withdrawal by SOC and PT

In the overall summary of TEAEs table (i), besides tabulating the number and percentage of subjects, the total number of TEAE episodes will also be provided. If a subject has repeated episodes of a particular TEAE, all episodes will be counted in the summary table.

In the remaining summary tables, the incidence of TEAEs will be calculated by dividing the number of subjects who have experienced the event by the total number of subjects in the safety set. Thus, the incidence of TEAEs is shown in terms of the total number of subjects and not in terms of the total number of episodes. If a subject has repeated episodes of a particular TEAE, only the most severe episode, or the episode with the strongest causal relationship to study drug, will be counted in the summary tables.

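### For an isolated aminotransferase rise, the only timed re-test follows a relatedness call by unblinded assessors, so unscheduled and confirmed liver findings may be ascertained unequally between CRV431 and placebo

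*Combined protocol and SAP*

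**What the plan says.** **Re-test pathway.** The hepatic part of Protocol 7.7.1 opens "For subjects experiencing any hepatic AEs or SAEs judged by the investigator or sponsor to be related to study drug". Under that lead-in come three things:

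- "Repeat testing of ALT, AST, ALP, TBL will be performed within 48-72 hours to confirm the abnormality".
- For an event meeting the section's definition of drug-induced liver injury (aminotransferases > 3 x ULN or > 3 x baseline), "the frequency of blood chemistries will increase to daily, if appropriate".
- If the elevation persists on repeat, close observation and/or consideration of stopping drug.

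Section 7.8 is entered after detection and confirmation, refers back to 7.7.1, and includes "Repeating liver enzyme and serum bilirubin tests 2 or 3-times weekly".

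**Who judges.** Section 7.3.3: "This is a single blind study where the investigator and sponsor are unblinded". Section 11.3 asks for causality against the investigational product, and 12.2.2 names study drug and placebo separately.

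**Liver rules with no causality condition.**

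- The interruption thresholds later in 7.7.1 use multiples of baseline and order no repeat test.
- Section 8.3.1 withdraws subjects for confirmed, non-cholestatic ALT with raised bilirubin, and does not say how ALT is confirmed.
- Section 11.1.6.2 adds a GGT test for "Subjects with normal ALT and bilirubin at baseline who have ALT >3 x ULN and bilirubin >2 x ULN", with a parallel rule for ALT already raised at baseline.
- Section 11.4 wants every adverse event followed until it resolves or stabilizes, or until an agreed time. It sets no interval.

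**Analysis.** Table 3 and 11.1.6 give all subjects the same scheduled chemistry. SAP 7.3 summarizes laboratory data by treatment group and visit. SAP 7.2.5 tabulates "the number and percentage of subjects experiencing a TEAE by SOC, PT and the highest severity". SAP 4.3 says "All data will be included in the analysis based on the visit as it is recorded in the database", and the visible SAP text has no rule that separates unscheduled results.

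**The concern.** The first primary objective compares safety with placebo. Subjects may enter with raised transaminases: the enzyme exclusion requires > 5 x ULN together with ALP > 2 x ULN, and 7.7.1 itself provides for baselines of 5 x ULN or more. Spontaneous fluctuation past a threshold is therefore plausible in either arm, and the placebo experience is what events on CRV431 will be read against.

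An assessor who knows that a subject is on placebo would not be expected to attribute a rise to CRV431. The same laboratory value can then lead to a re-test within three days in one subject and to no set re-test time in another. Extra tests can raise the recorded CTCAE grade, show a higher peak or reveal a second abnormality. This concerns how much testing takes place, which is separate from unblinded grading of results already in hand.

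**Working it through.** The plan states no figure on this point, so there is none to reproduce. The check has three steps.

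**1. Which rules order a repeat liver test, and on what condition?**

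| Protocol section | Causality needed? | Repeat test for an isolated rise? |
|---|---|---|
| 7.7.1, hepatic events | Yes | Yes, 48-72 h; daily chemistry if appropriate |
| 7.8 | By reference to 7.7.1 | Yes, after confirmation |
| 7.7.1, interruption thresholds | No | None ordered |
| 8.3.1, ALT plus bilirubin | No | Confirmation required, procedure not given |
| 11.1.6.2 | No | GGT only, and only with raised bilirubin |
| 11.4 | No | Follow-up, no interval |

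For an isolated aminotransferase rise, the only timed re-test sits behind the relatedness judgement.

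**2. How long until the next routine chemistry?** From the visit days and windows in 7.1.2, 7.1.3 and Table 3:

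- Day 2 to 7: 5 days (range 4-6)
- Day 7 to 14: 7 days (5-9)
- Day 14 to 28: 14 days (13-17)
- Day 28 to 42: 14 days (10-16)

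After a Day 14 finding judged related, the repeat falls on Day 16-17. Daily chemistry on Days 15-27 would add at most 27 - 15 + 1 = 13 draws. Without that judgement, the next scheduled draw is Day 28.

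**3. What could a routine visit miss?** The documents give no duration for such rises. Assume that the time a rise persists after detection is exponential with mean m days, that the re-test comes at 2.5 days (midpoint of 48-72 h), and that there is no discretionary recheck. Among rises that the re-test would confirm, the share gone by the next routine visit at gap g is

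1 - exp(-g/m) / exp(-2.5/m) = 1 - exp(-(g - 2.5)/m).

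Examples: g = 14, m = 7 gives 1 - exp(-11.5/7) = 1 - 0.193 = 81%. With g = 5, m = 30 it is 1 - exp(-2.5/30) = 1 - 0.920 = 8%.

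| Gap g | m = 3 | m = 7 | m = 14 | m = 30 |
|---|---|---|---|---|
| 5 days (after Day 2) | 57% | 30% | 16% | 8% |
| 7 days (after Day 7) | 78% | 47% | 27% | 14% |
| 14 days (after Day 14 or 28) | 98% | 81% | 56% | 32% |

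On the scale of this trial, assume that 10% of subjects have a rise and that 80% of re-tests confirm it (neither figure is in the documents). The 12 placebo subjects would then yield 12 x 0.10 x 0.80 = 0.96 confirmed rises if all are re-tested and 0.48 if half are. The chance of at least one is 1 - 0.92^12 = 63% and 1 - 0.96^12 = 39%, respectively.

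**The case against.** Much of the case on the other side stands.

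- **Follow-up is owed in both arms.** Section 11.4 requires follow-up of every adverse event whatever its cause, 11.1.6 allows local testing, and 11.1.6.1 to 11.1.6.3 foresee rechecks. The difference is in timing and uniformity. A reader might infer that a placebo rise is never re-tested; the documents do not say so.
- **Re-testing on CRV431 is not assured.** A rise attributed to underlying NASH also falls outside the pathway. Nor does the text bar a placebo event from being called related: 7.3.1 uses study drug loosely for either capsule.
- **First detection is protected.** Scheduled chemistry is the same in every cohort, and SAP 7.2.5 counts a subject once per event, so re-testing a known event adds no subject for that event.
- **Little in the outputs turns on confirmation.** The listed SAP tables show no comparison of confirmed elevations. The aminotransferase criterion in 7.7.2 itself requires relatedness, so an unconfirmed placebo rise would not change it.
- **Direction is open.** A reader might infer bias against the drug. A repeat can clear an abnormality as well as confirm it, so this is not shown.
- **The percentages depend on the assumed duration.** A 60-day mean gives 4%, 7% and 17% for gaps of 5, 7 and 14 days. The 13 draws are a ceiling, since daily testing is conditional and testing may become less frequent once drug is stopped.

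The GGT rule is a different test on a different condition, so it does not contradict 7.7.1; it shows only that the protocol elsewhere acts on the laboratory value. The public copy also flattens the bullets in 7.7.1 and does not show the Table 3 footnote on chemistry, so this reading of the nesting is the natural one but not certain.

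**Conclusion.** The point holds in limited form. For isolated aminotransferase elevations, timed confirmation, optional daily chemistry and entry to close observation depend on a relatedness judgement by people who know the arm. The sections that use confirmed ALT, act on values, or require follow-up do not fill the gap in a uniform way. Highest grade, peak value, second abnormalities and the status of a rise as confirmed may therefore be ascertained unequally between CRV431 and placebo.

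Summaries of scheduled-visit values are not affected, and the placebo liver data remain interpretable at those visits. Neither direction nor size can be established from the documents. The missed share runs from 16-98% for assumed mean durations of 3-14 days down to 8-32% at 30 days. Both ranges assume exponential persistence and no discretionary recheck.

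**What to change.** **SAP 7.2.5 and 7.3.** Add a between-arm summary of ALT, AST, ALP and bilirubin elevations (incidence above multiples of ULN or baseline, and peak value) from scheduled visits only, built identically for Cohorts A to D. Show it alongside the summary of all values. Flag laboratory TEAEs that were first detected, or raised in grade, only on an unscheduled test. The cost is one more table and a flag. The scheduled-visit summary leaves out unscheduled peaks, which stay in the all-values summary and the listing.

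**Protocol.** The sponsor must reconcile 7.7.1, 7.8, 8.3.1, 11.1.6.2 and 11.4 on when a liver abnormality is re-tested and what counts as confirmed, and state whether this applies in the same way in all four cohorts. This is a wording amendment; any extra blood draws depend on what the sponsor decides. No trigger, threshold, test frequency or dosing rule is proposed here.

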7.7.2. Study Criteria

Dosing of study drug within the study will be stopped and recruitment into the study will be paused until a review of all available safety information is performed by the DSMB, Medical Monitor, and Sponsor if any of the following occur:

- \geq 3 subjects in the study experience an SAE that is judged to be related to study drug by the investigator and sponsor;
- \geq 3 subjects in the study experience a Grade 3 or Grade 4 CTCAE AE in the same system organ class (SOC) that are judged to be related to study drug by the investigator and sponsor;
- \geq 3 subjects in the study experience a Grade 3 or Grade 4 CTCAE laboratory abnormality that are judged to be related to study drug by the investigator and sponsor. Asymptomatic elevations in cholesterol or triglycerides accepted;
- \geq 3 subjects in the study experience a confirmed:
 - Friderica's QT Correction Formula (QTcF) interval \geq 500 msec;
 - OR

- QTcF interval change from baseline ≥ 60 msec that has an absolute value ≥ 480 msec;
 - The value of an individual ECG time point is the average of the triplicate values
 - “confirmed” is defined as the abnormality duplicated, at least 1 hour after the abnormality is first noted, by the results of a set of 3 ECGs performed in triplicate, at least 5, but not more than 10 minutes between each assessment.
- ≥ 1 subject with AT > 3 x ULN or > 3 x subject baseline that is confirmed, not initially cholestatic, and judged to be adversely related to study drug (DILI) by the investigator and sponsor.

7.7.2.1. Study Stopping Criteria

Study will be stopped and a review of all available safety information is performed by the DSMB, Medical Monitor, and Sponsor if any of the below criteria is met:

- ≥ 1 subject develops a Grade 5 CTCAE adverse event attributed to CRV431
- ≥ 2 subjects develop a Grade 4 CTCAE adverse event attributed to CRV431
- ≥ 3 subjects develop the same Grade 3 CTCAE adverse event attributed to CRV431

The study may be restarted depending on the specific AE, relationship to the study drug and with the agreement of the DSMB, Medical Monitor and Sponsor.

7.7.3. Pharmacokinetic Criteria for Dose Adjustment

Dose adjustment is not available for subjects in Cohort A receiving 75 mg of CV431 QD. If a patient demonstrates adverse events that trigger the need for stopping, that patient will be stopped and an additional patient will be started on the same dose unless the study data indicates a problem with the dose level as recommended by the DSMB. Subjects in Cohort C, receiving 225 mg of CRV431 QD, experiencing a drug exposure related Grade 3,4 or 5 CTCAE can have a dosage reduction to 150 mg of CRV431 once daily.

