8.3. Subject Withdrawal Criteria

8.3.1. Early Termination of Subjects from the Study

Subjects who discontinue the study should complete all scheduled safety assessments at the Early Termination Visit. If an Early Termination Visit and a scheduled visit coincide, procedures for both visits should be completed, without duplication. Subjects must discontinue the study for the following reasons:

- Subject withdraws consent;
- Subject unwilling or unable to follow study procedures, per judgment of the investigator;
- Investigator, sponsor, or Regulatory Authority judge that further dosing with study drug would be harmful to the subject;
- Subject experiences an SAE that is judged, by the investigator and the sponsor, to be related to study drug;
- Subject experiences a Grade 3 CTCAE AE judged, by the investigator and the sponsor, to be related to study drug;
- Subject experiences a Grade 4 CTCAE AE judged, by the investigator and the sponsor, regardless of the relation to study drug;
- Subject experiences a Grade 3 or Grade 4 CTCAE laboratory abnormality judged by the investigator and the sponsor, to be related to study drug except for asymptomatic elevations in cholesterol or triglycerides which are accepted;

- Subject with normal ALT and bilirubin at baseline who experiences confirmed, non-cholestatic ALT $>3 \times$ ULN and bilirubin $>2 \times$ ULN OR subjects with elevated ALT at baseline who experiences confirmed, non-cholestatic ALT $>10 \times$ baseline value and bilirubin $>2 \times$ ULN;
- Subject experiences a confirmed,
 - QTcF interval 500 msec;
OR
 - QTcF interval change from baseline ≥ 60 msec that has an absolute value ≥ 480 msec. The value of an individual ECG time point is the average of the triplicate values
 - “confirmed” is defined as the abnormality duplicated, at least 1 hour after the abnormality is first noted, by the results of a set of 3 ECGs performed in triplicate, at least 5, but not more than 10 minutes between each assessment;
- Subject experiences any hepatic AE or SAE judged by the investigator or sponsor as DILI and to be related to study drug and not to the subject’s underlying NASH.

Subjects who discontinue the study due to the safety stopping criteria will be replaced if the investigator and sponsor agree and the criteria outlined in Section 7.5 are not violated. Subjects who discontinue the study for non-safety reasons may be replaced.

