8.4. Subject Replacement

Subjects who do not complete the study may be replaced, at the sponsor’s discretion to ensure that the study is fully populated, unless a stopping rule precludes replacement. Replacement subjects will receive the same treatment assignment as the subject they are replacing. Each enrolled subject may only participate in this study once. The study is designed to have 12 subjects on active treatment and 6 subjects on placebo to complete the study.

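### Protocol 7.7.3 lets a Cohort C subject continue at 150 mg after a related Grade 3 or 4 event, while 8.3.1 requires the same subject to discontinue

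*Combined protocol and SAP*

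**What the plan says.** Section 7.7.3 of the protocol treats the two dose levels differently. It offers no dose adjustment in Cohort A (75 mg). A sentence on stopping follows: should adverse events "trigger the need for stopping, that patient will be stopped and an additional patient will be started on the same dose". That sentence gives way only where the data point to trouble with that dose level. The section's last sentence concerns Cohort C, where a subject "experiencing a drug exposure related Grade 3,4 or 5 CTCAE can have a dosage reduction to 150 mg of CRV431 once daily".

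Section 8.3.1 opens its list with "Subjects must discontinue the study for the following reasons". Two entries matter here. The first covers related Grade 3 events: "Subject experiences a Grade 3 CTCAE AE judged, by the investigator and the sponsor, to be related to study drug". The second covers Grade 4 events: "Subject experiences a Grade 4 CTCAE AE judged, by the investigator and the sponsor, regardless of the relation to study drug". The list covers all subjects. The only carve-out in its Grade 3 and 4 rules is for symptom-free cholesterol or triglyceride elevations, and it sits in the entry on laboratory abnormalities.

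Section 7.7.1 names Grade 3 or higher events possibly or probably related to study drug, and any Grade 4 event, as stopping criteria for an individual subject. If one is met, "then no further dosing will occur at any of the study sites until a review of all available safety information is performed". The DSMB, Medical Monitor and Sponsor carry out that review. If dosing is later judged safe, an application for a substantial amendment goes to regulators and ethics committees, where applicable. Under Section 7.7.2.1, a single Grade 5 event attributed to CRV431 stops the study.

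**The concern.** A site with a Cohort C subject who has a related Grade 3 or Grade 4 event finds a permission to reduce the dose in one section and an obligation to discontinue in another. Neither section refers to the other on this point, and no text says which prevails.

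This is a subject-level safety rule at the higher dose, in what Section 5.4 calls the first study of CRV431 in this population. Safety and tolerability is a primary objective (Section 6.1). Investigator and sponsor are unblinded (Section 7.3.3), so whoever chooses between the rules would know the assignment.

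The choice also decides how the event is reported. The readable AE summaries and listing in SAP 7.2.5 identify events that led to withdrawal but have no entry for dose reduction.

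**Working it through.** There is no planned figure to reproduce, because the point depends on no sample size, power or error rate. The check sets the rules side by side for one Cohort C subject.

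| Event | 7.7.3 | 8.3.1 | 7.7.1 |
|---|---|---|---|
| Grade 3, judged related by investigator and sponsor | May reduce to 150 mg | Must discontinue | Dosing halted everywhere pending review |
| Grade 4, drug-exposure related | May reduce to 150 mg | Must discontinue, whatever the cause | Dosing halted everywhere pending review |
| Grade 5 (death) | May reduce to 150 mg | Not applicable | Dosing halted everywhere; 7.7.2.1 also stops the study if attributed to CRV431 |

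The first two rows conflict. The third is a drafting slip, since a fatal event cannot lead to a lower dose.

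Three ways of reconciling the sections were tried.

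1. The obligation in 8.3.1 overrides the permission in 7.7.3. The sentence in 7.7.3 would then survive only for marginal cases, such as a Grade 3 event that only one of investigator and sponsor judges related, or an exempt lipid elevation. It is not worded to cover only those. For Grade 4 adverse events relatedness makes no difference under 8.3.1.
2. The stopping sentence in 7.7.3 ("trigger the need for stopping, that patient will be stopped and an additional patient will be started on the same dose") covers both dose levels. It speaks of a patient in general, so this is possible. The next sentence then allows reduction for the grades that trigger stopping. The sentence also directly follows the one on Cohort A and may be limited to it. In that case it does nothing to resolve the conflict for Cohort C.
3. The 7.7.1 review decides. It determines whether and when dosing restarts, but does not say whether the affected subject may return, or at what dose.

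None of the three settles the matter.

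Consequence for one such event:

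- Dose: Cohort C takes 3 × 75 mg = 225 mg (Section 7.3). The reduced dose is 2 × 75 mg = 150 mg, and 150/225 = 0.667.
- Replacement: under 8.3.1, subjects who leave for safety "will be replaced if the investigator and sponsor agree and the criteria outlined in Section 7.5 are not violated". Under Section 8.4, "Replacement subjects will receive the same treatment assignment as the subject they are replacing". One more person may therefore be exposed to 225 mg.
- Reporting: assume that all 12 planned Cohort C subjects are dosed and that percentages are taken within the dose group. This event alone then adds 0/12 = 0% to the table of TEAEs leading to withdrawal if the dose is reduced. If the subject discontinues, it adds 1/12 = 8.3% without replacement, or 1/13 = 7.7% with one replacement.

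These fractions count only the affected subject. No number of other subjects completing at 225 mg can be given, because 7.7.1 would interrupt dosing for everyone then on treatment.

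**The case against.** The strongest reply is that the protocol already leans towards stopping. Section 7.7.1 classes these events as stopping criteria, 7.7.3 itself has a sentence saying the patient is stopped, and 8.3.1 is mandatory. Against these stands one permissive clause, and a cautious site would discontinue. This stands as a description of the likely default. It does not remove the clause or say when it applies.

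A reader might infer that an investigator could quickly put a subject back on CRV431 after a related Grade 4 event on the strength of 7.7.3 alone. The documents do not support that. The 7.7.1 halt, the three-party review and the amendment application, where applicable, all come first. Treatment lasts only 28 days, and missing more than 2 consecutive doses is itself a ground for considering discontinuation or interruption. A restart at 150 mg would be hard to achieve in that time.

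A reader might also infer that a dose reduction would go unrecorded. That is not so. Protocol Section 11.4 has the investigator report the action taken for each adverse event, the event is tabulated by severity and relationship under either rule, and the exposure summary in SAP 7.1 would show fewer capsules. Parts of the SAP are also redacted. What remains is that the readable withdrawal table counts the event under one rule and not under the other.

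**Conclusion.** The point holds as an internal contradiction between two readable protocol sections. For a Cohort C subject with a Grade 3 event that investigator and sponsor judge related, or with a drug-exposure-related Grade 4 event, 7.7.3 permits continued treatment at two thirds of the dose and 8.3.1 forbids it. The conclusion assumes only that an event described as drug exposure related, a term not defined in the readable text, is related to study drug in the sense of 8.3.1. For Grade 4 even that assumption is unnecessary.

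The effect is confined to the affected subject's treatment, possible replacement and place in the withdrawal table. Its frequency cannot be estimated from the documents. No power or error-rate figure changes, since the sample size has no statistical basis and the data are summarised descriptively. The wording still needs correction, because sites cannot follow both rules.

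**What to change.** In 7.7.3, delete Grades 4 and 5 from the Cohort C sentence and state that 8.3.1 governs. A Grade 3 event judged related by investigator and sponsor then leads to discontinuation, and reduction to 150 mg remains only for events that meet no 8.3.1 criterion.

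If the sponsor does intend reduction after related Grade 3 events, it should instead write an explicit Cohort C exception into 8.3.1, applying only after the 7.7.1 review by the DSMB, Medical Monitor and Sponsor. In either case, say whether the stopping sentence in 7.7.3 applies to both dose levels. If the exception is adopted, a summary row for TEAEs leading to dose reduction would be a useful but optional addition to SAP 7.2.5.

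The cost is amendment wording and a check against the DSMB charter. No patients or procedures are added.

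A separate editorial correction can go in the same amendment. The synopsis and Sections 7.1.3 and 8.3.1 point to Section 7.5 for stopping or dose-adjustment rules. Section 7.5 is the COVID-19 vaccine section, so the pointers should read 7.7.
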